## **3.3.** Exclusion Criteria

Potential subjects who meet any of the following criteria will be excluded from participating in the study:

Exclusion Criteria after Screening:

- 1. Currently pregnant or breastfeeding.
- 2. Any ocular or systemic allergies or diseases that may interfere with contact lens wear.
- 3. Any autoimmune disease or use of medication, which may interfere with contact lens wear. Habitual medications used by successful soft contact lens wearers are considered acceptable.
- 4. Entropion, ectropion, extrusions, chalazia, recurrent styes, glaucoma, history of recurrent corneal erosions, or aphakia.
- 5. Any previous, or planned, ocular or interocular surgery (e.g., radial keratotomy, PRK, LASIK, etc.).
- 6. Any corneal distortion resulting from previous hard or rigid gas permeable contact lens wear.
- 7. Multifocal, toric or extended wear contact lens correction.
- 8. Participation in any contact lens or lens care product clinical trial within 14 days prior to study enrollment.
- 9. History of binocular vision abnormality or strabismus.
- 10. Any infectious disease (e.g., hepatitis, tuberculosis) or contagious immunosuppressive diseases (e.g., HIV) by self-report.
- 11. Employee or immediate family member of an employee of clinical site (e.g., Investigator, Coordinator, Technician).

Exclusion Criteria after Baseline

- 12. Any ocular infection.
- 13. Any grade 3 or greater slit lamp findings (e.g., edema, corneal neovascularization, corneal staining, tarsal abnormalities, conjunctival injection) on the FDA classification scale, any previous history or signs of a contact lens-related corneal inflammatory event (e.g., past peripheral ulcer or round peripheral scar), or any other ocular abnormality that may contraindicate contact lens wear.

#### **3.4.** Enrollment Strategy

Study subjects will be recruited from the Institution/clinical site's subject database and/or utilizing Independent Ethics Committee (IEC) or Institutional Review Board (IRB) approved materials.

## 4. STUDY DESIGN AND RATIONALE

#### 4.1. Description of Study Design

The study is a single-site, controlled, randomized, subject-masked, non-dispensing, contralateral design. The study begins with an initial visit (Visit 1 - Day 0), if a subject is found to meet all eligibility criteria, then they will be randomized to one of two lens wear sequences (Left: Test, Right: Control or Left: Control, Right: Test); otherwise a subject will be deemed ineligible for this study.

If a subject is found eligible and was 'dispensed' study lenses at the initial visit, then one additional visit will occur. Visit 2 will occur no sooner than 24 hours after Visit 1 and no later than 28 days after visit 1. Each visit will last approximately 2-3 hours each. Unscheduled visits may occur during the course of the study.

## 4.2. Study Design Rationale

This study will be executed using a contralateral design. There are several benefits to this choice of design. First, we intend to relate performance with the investigational lens in its activated and inactivated states to baseline light sensitivity. A contralateral design will allow us to compare performance with both activation states within the same individual, ostensibly with the same baseline light sensitivity. Second, other subject factors that can influence visual performance, such as iris color and absorption of test lights via macular pigment, are better controlled using this design. Third, in psychophysical testing, which is the gold standard for many of the visual functions being tested, participants make judgments about some event threshold, such as when an image disappears or how large or bothersome or intense a visual event appears. Participants may have different criteria for threshold events that are internally consistent *within* subjects but can vary *between* subjects. A contralateral design allows the investigational lens to be compared within subjects, with consistent criteria for threshold events. Given the fact that sufficient time will be taken between measures, in some cases 24 hours or more, carryover effects are unlikely.

## 4.3. Enrollment Target and Study Duration

Approximately 66 subjects will be enrolled to complete approximately 60 at a single site. The point of study enrollment is the execution and completion of the signed Informed Consent document. Subjects will be stratified into one of two age groups using a 2:1 allocation ratio:

- 40 subjects ±3 in age group 18-39
- 20 subjects ±3 in age group 40-65

There are two study visits that will last approximately 2-3 hours each. At least 24 hours must separate the end of Visit 1 and the beginning of Visit 2. Once enrolled, all subjects are expected to complete both visits within 28 days. The study enrollment period will be approximately 6 weeks.

## 5. TEST ARTICLE ALLOCATION AND MASKING

## 5.1. Test Article Allocation

Use of the test articles will be randomized using a randomization scheme supplied by the study biostatistician.

This is a single-site, two-visit, contralateral, subject-masked, non-dispensing and randomized study. The study lenses will be worn in a contralateral and random fashion. At visit 1, a block size of (2) sequences will be used to randomly assign subjects to one of two lens wear sequences (Left: Test, Right: Control or Left: Control, Right: Test).

At visit 2, there are two levels of randomization, a block size of (2) sequences will be used to randomly assign subjects to one of two lens wear sequences (Left: Test, Right: Control or Left: Control, Right: Test). Once subjects are randomized to a lens wear sequence, subjects will then be randomized to the order of Test lens activation (activated/inactivated or inactivated).

The random scheme for each visit will be generated by site using the PROC PLAN procedure from SAS Software Version 9.4 or higher (SAS Institute, Cary, NC).

The study site must follow the randomization scheme provided and complete enrollment according to the randomization list and not pre-select or assign subjects. The randomized assignment of subjects will be performed at the first visit prior to the first fitting. The following must have occurred prior to randomization:

- Informed consent has been obtained
- Subject meets all the inclusion / exclusion criteria
- Subject history and baseline information has been collected

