## 5.2. Masking

This is a subject-masked study. Masking will be used to reduce potential bias. Subjects will be unaware of the identity of the investigational product. Investigators and clinical site personnel involved in the data collection will not be masked as to the identity of the investigational product. Although the subjects will not be aware of which study lens is going on which eye, the dynamic nature of the test lens during the assessments may give the identity.

Under normal circumstances, the mask should not be broken until all subjects have completed the study and the database is finalized. Otherwise, the mask should be broken only if specific emergency treatment/course of action would be dictated by knowing the treatment status of the subject. In such cases, the Investigator may, in an emergency, contact the medical monitor. In the event the mask is broken, the Sponsor must be informed as soon as possible. The date, time, and reason for the unmasking must be documented in the subject record. The Investigator is also advised not to reveal the study treatment assignment to the clinical site or Sponsor personnel.

Subjects who have had their treatment assignment unmasked are expected to return for all remaining scheduled evaluations. Subjects who are discontinued will be replaced.

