## 5.3. Procedures for Maintaining and Breaking the Masking

The identity of the study lenses will be masked to the subjects by over labeling the blister pack of the study lens. The label will contain the study number, lot number, sphere power, expiration date and the randomization codes S and N.

The test articles mask shall not be broken unless information concerning the lens type is necessary for the urgent medical treatment of a subject. The Sponsor must be notified before the mask is broken.

When dispensing test articles, the following steps should be followed to maintain randomization codes:

- 1. Investigator or designee (documented on the Delegation Log) will consult the lens fitting schedule/randomization scheme to obtain the test article assignment for that subject prior to dispensing
- 2. Investigator or designee will record the subject's number on the appropriate line of the randomization scheme
- 3. Investigator or designee will pull the appropriate test articles from the study supply. All test articles that are opened, whether dispensed (placed/fit on eye or dispensed outside the clinical site) or not, must be recorded on the Test Article Accountability Log in the "Dispensed" section

Subjects who have had their treatment assignment unmasked are expected to return for all remaining scheduled evaluations. Subjects who are discontinued may be replaced.

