1.27	Exit Slit Lamp Biomicroscopy	
 
FDA Slit Lamp Classification Scale will be used to grade the findings and determine eligibility.
 
Ocular adverse events shall be those that grade 3 or 4 on the FDA scale. The study monitored must be notified immediately. The AE will be followed to resolution at which time the subject will be terminated from the study.
 
If the clearance of the fluorescein needs to be expedited, preservative-free rewetting drops or saline may be instilled.
 
		
1.28	Exit VA	Record subjects' distance Snellen visual acuity, OD, OS, and OU to the nearest letter with their habitual correction in place (spectacles or contact lenses). Schedule Visit 2 at least 24 hours and no more than 28 days from now.		

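### Visit 2 lens-to-eye assignment, behind all six primary contrasts, uses disclosed fixed blocks of 2 on a list read by unmasked site staff, with no concealment step and contradictory statements on when it is made

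*Combined protocol and SAP*

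**What the plan says.** Section 5.1 describes a fresh allocation for the second visit: "At visit 2, there are two levels of randomization, a block size of (2) sequences will be used to randomly assign subjects" to Test on the left eye and Control on the right, or the reverse. Activation order is randomised afterwards. Each visit has its own scheme: "The random scheme for each visit will be generated by site using the PROC PLAN procedure from SAS Software Version 9.4 or higher". The study biostatistician supplies it, so "by site" most likely means per site.

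Section 5.3 says how the scheme is used. The investigator or designee "will consult the lens fitting schedule/randomization scheme to obtain the test article assignment for that subject prior to dispensing" and then "will record the subject's number on the appropriate line of the randomization scheme". Nothing says which line is the appropriate one. No envelope, interactive system or one-at-a-time release is mentioned. Section 5.2 adds: "Investigators and clinical site personnel involved in the data collection will not be masked as to the identity of the investigational product".

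On timing, section 5.1 also says: "The randomized assignment of subjects will be performed at the first visit prior to the first fitting". The synopsis and the sentence on two levels of randomisation place the Visit 2 assignment at Visit 2. Step 2.6 in section 7.2 assigns the lens from the scheme at that visit, and step 2.17 carries the title Sequence Randomization. Step 1.28 has the site book the second visit: "Schedule Visit 2 at least 24 hours and no more than 28 days from now".

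Section 5.1 also tells the site to follow the list and forbids it to choose subjects for particular assignments.

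**The concern.** In a contralateral comparison each subject wears both lenses, so differences between subjects drop out but differences between a subject's two eyes do not. Random assignment of lens to eye is what stops the Test lens from going more often to the better eye. That protection needs the next assignment to be unknown when a subject is matched to it.

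Here the block size is printed in the protocol, one site enrols everyone, and its staff know the previous assignment and read the list. The same Visit 2 assignment carries the two-point threshold, halo and starburst comparisons in both activation states, so any imbalance between eyes would enter all six primary contrasts.

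The timing conflict bears on how much this matters. If the Visit 2 assignment is fixed at Visit 1 before any study lens is fitted, the Visit 1 results cannot influence it. If it is made at Visit 2, and lines are used in the order in which subjects return, the site could already hold Visit 1 results for each eye (section 15.1 has them calculated and entered at the site). It also books the return within a 28-day window.

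The primary model in section 14.5 contains sequence, lens type, age group, dominant eye and lens type by age group. It has no baseline measure for each eye, so it would not remove an imbalance tied to an eye's own performance.

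**Working it through.** **Inputs from the documents.** Block size 2 (5.1). Target of 60 completers from 66 enrolled (14.2). Three endpoints in two activation states, so 3 × 2 = 6 primary contrasts (2.3, 14.5). A two-sided 95% interval for each contrast (14.5), so 2.5% error in the direction favouring Test. Section 14.2 reports no power calculation, and no SD or between-eye correlation is given, so the plan has no figure of its own to reproduce.

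**Predictability.** In a block of 2 the first assignment is a coin toss and the second is certain.

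- Share certain: 1/2, which is 30 of 60 (33 of 66).
- Best guess correct: (0.5 + 1)/2 = 75%, which is 45 of 60 (49.5 of 66).
- Block of 4: (1/2 + 2/3 + 2/3 + 1)/4 = 70.8% correct, 33.3% certain.
- Block of 6, by enumeration: 68.3% correct, 25.0% certain.
- Simple randomisation: 50% correct, none certain.
- List visible: 100% for any block size.

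Larger blocks alone therefore gain little.

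**Consequence if the order within a pair were chosen.** Two quantities have to be assumed:

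- f: the share of adjacent pairs in which the site picks which subject takes which of the two opposite lines.
- rho: the correlation between the between-eye difference known to the site and the between-eye difference at Visit 2.

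The expected smaller of two independent standard normal values is −1/√π = −0.564. So, in SDs of the between-eye difference:

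bias towards Test ≈ 0.564 × f × rho

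The false-benefit rate comes from simulation: 20,000 runs, 60 subjects, no true lens effect, and a within-subject t test adjusted for sequence.

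| rho | f | Bias by formula (SD) | False-benefit rate |
|---|---|---|---|
| any | 0 | 0 | 2.5% (nominal) |
| 0 | any | 0 | 2.5% (nominal; simulated 2.3% to 2.7%) |
| 0.1 | 0.25 | 0.564 × 0.25 × 0.1 = 0.014 | 3.1% |
| 0.3 | 0.25 | 0.564 × 0.25 × 0.3 = 0.042 | 5.1% |
| 0.5 | 0.25 | 0.564 × 0.25 × 0.5 = 0.071 | 7.9% |

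The most extreme setting discussed below (rho 0.7, f 0.5) gives about 34%.

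**Timing statements side by side.** The synopsis, the two-level sentence in 5.1 and step 2.17's title point to Visit 2. The sentence quoted from 5.1 on the first visit points to Visit 1. Step 2.6 fits either reading, since it could simply apply an assignment already made. Nothing in 5.1, 5.3 or 7.2 settles the matter or says that lines are used in order of return.

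**The case against.** A reader might infer that the Visit 2 assignment is made after each eye's results are known, in an order the site controls, and so will be steered. The documents do not support that.

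- Section 5.1 can be read as fixing all assignments before any study lens is fitted, which would close the route through Visit 1 results.
- Booking Visit 2 matters only if lines are used in order of return, and no text says so. Section 5.3 refers to the assignment for a given subject, which also fits a line tied to that subject.
- Section 5.1 forbids pre-selection. A value of f at 25% or more means deliberately breaking that rule in a quarter or more of pairs, with both subjects of a pair awaiting Visit 2 together.
- A co-investigator does the psychophysical testing, and the subject then returns to the principal investigator to finish the visit (steps 1.25 to 1.28). Squint is read from still frames of video and may not be available at booking.
- Visit 1 eye differences mix lens effect, eye effect and noise. They come from different tests than the Visit 2 primaries, and section 1 itself separates veiling glare from halos and spokes. A low rho is plausible.
- The simulation adjusts for sequence only. It is not the full planned mixed model.

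These points rule out treating steering as a feature of the plan or an inflation of around 34% as expected. They do not restore concealment. An instruction not to pre-select is not concealment, and the separation of roles is not a formal barrier. Unmasked staff know which eye wore which lens, so the Visit 1 information is weakened rather than lost. The block size and the site's use of the list stand as written.

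**Conclusion.** The point holds as a weakness in allocation concealment together with an internal contradiction. From the text alone, half of the Visit 2 assignments can be known in advance from the block size, 75% can be guessed correctly, and all are known if the list is visible. No concealment step is described, the timing statements conflict, and the rule linking subjects to lines is missing.

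The effect on the results is conditional. It requires assignment at Visit 2, lines used in order of return, deliberate reordering, and a between-eye difference that carries over to the Visit 2 endpoints. Under the assumed values of 25% of pairs and rho from 0.1 to 0.5, the false-benefit rate per contrast moves from 2.5% to between about 3% and 8%. It does not move if f or rho is zero, and much larger figures need extreme assumptions. The change is worth making because it is cheap and the assignment supports every primary comparison.

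**What to change.** 1. Reconcile the timing statements in 5.1, the synopsis and steps 2.6 and 2.17, so that one moment of assignment is stated for each visit.
2. Have the biostatistician generate one list in which each subject number carries its Visit 1 sequence, Visit 2 sequence and Visit 2 activation order, fixed before any measurement. The order of return for Visit 2 then cannot change an assignment, and the link from subject to line is explicit.
3. Keep the list from the site. Release the Visit 1 part only after eligibility is entered at step 1.13, and the Visit 2 part only after continuance is entered at step 2.5. Use numbered sealed envelopes, or the EDC system if it has that function; section 15.1 does not describe one.
4. As a minor addition, use mixed block sizes that are not disclosed to the site. Block sizes of 4 or 6 on their own lower best-guess accuracy only to about 68% to 71%, so this does not replace step 3.
5. Reword 5.1, 5.3 and steps 1.14 and 2.6 to match.

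The cost is a regenerated list, short wording changes, a brief release step at each visit and slightly looser balance between the two sequences. No extra subjects are needed.

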# 14.5. Primary Analysis

# Light Scattering (Two-point Light Spread Function)

This is defined as the minimum distance (mm) that two points of light are completely distinct. This threshold will be analyzed by a linear mixed model. Sequence of lens wear, lens type, age group, dominant eye and the interaction between lens type and age group will be included in the model as fixed effects. An appropriate covariance structure will be used to model the residual errors between measurements between eyes within a subject. The variance-covariance structure will be selected based on the finite-sample corrected Akaike's Information Criterion Corrected (AICC). The structure that returns the lowest AICC will be deemed the most appropriate structure. Covariance structures under consideration include:

- Unstructured (UN)
- Compound Symmetry (CS)
- Heterogeneous Compound Symmetry (CSH)

Heterogeneous covariance structures across lens type may be considered if necessary. The Kenward and Roger method (Kenward and Roger, 1997) will be used for the denominator degrees of freedom.

Comparisons between lenses (Test inactivated vs Control and Test activated vs Control) will be carried out using 2-sided 95% confidence intervals constructed for the least-square mean (LSM) difference (Test – Control). Statistically significantly lower differences of the Test lens relative to the Control lens will be concluded if the upper limit of the 95% confidence interval is below 0. If the interaction between lens type and age is significant then comparisons between lenses will be made within age group.

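### Section 5.1 does not name age as a stratification factor for the lens-to-eye lists, so eye side can be uneven among the 20 or so older subjects and cost that group's contrast some precision

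*Combined protocol and SAP*

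**What the plan says.** **Enrolment (4.3).** "Subjects will be stratified into one of two age groups using a 2:1 allocation ratio": about 40 subjects aged 18-39, and "20 subjects ±3 in age group 40-65". The total is given as "Approximately 66 subjects will be enrolled to complete approximately 60 at a single site".

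**Allocation (5.1).** At each visit, "a block size of (2) sequences will be used to randomly assign subjects to one of two lens wear sequences" (Test on the left eye and Control on the right, or the reverse). At Visit 2, "subjects will then be randomized to the order of Test lens activation", with no block stated for that step. On how the lists are made: "The random scheme for each visit will be generated by site". There is one site. Age does not appear in 5.1.

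**Analysis (14.5, carried into 14.6).** "Sequence of lens wear, lens type, age group, dominant eye and the interaction between lens type and age group will be included" as fixed effects. There is no left/right eye term. Then: "If the interaction between lens type and age is significant then comparisons between lenses will be made within age group".

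**The concern.** Each subject wears Test in one eye and Control in the other, so within a subject lens and eye side cannot be told apart. Only balance of eye side across subjects separates them. Blocks of 2 secure that balance for the whole sample. They do not secure it inside an age group if one list serves both groups.

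The planned model does not repair this. With two lens sequences, a right-left difference appears as sequence by lens, and the model has only the main effect of sequence.

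The older-group contrast rests on about 20 subjects. If the interaction is significant it becomes a reported result, and an uneven split would carry part of any right-left difference into both that contrast and the interaction that triggers it.

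**Working it through.** The documents give no figure for balance within age group, and the sample size in 14.2 has no power calculation behind it, so there is no stated result to reproduce.

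**Inputs.** From the documents: 60 completers, 20 of them older (4.3); 1:1 lists in blocks of 2, separate at each visit (5.1). Assumed: one list covers both age groups; older subjects arrive in random order; a right-left difference of δ = 0.2, 0.3 or 0.5, in SDs of the paired Test-Control difference excluding the eye effect.

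**1. Chance of an uneven split.** A block holding two older subjects is balanced. A block holding one adds +1 or -1 to the imbalance. The exact distribution over 30 blocks gives:

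| Split of 20 older subjects | Chance per visit |
|---|---|
| exactly 10:10 | 22% |
| 12:8 or worse | 41% |
| 13:7 or worse | 17% |
| 14:6 or worse | 5.4% |

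- 13:7 or worse at one or both visits: 1 - (1 - 0.170)² = 31%.
- Range for 13:7 or worse by arrival pattern: 0% if all older subjects enrol consecutively (imbalance at most 2), up to 26% if each falls in a different block (binomial, n = 20).

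**2. Shift in the realised contrast.** Shift = (imbalance / 20) × right-left difference. At 13:7 this is 6/20 = 0.30 of the difference; at 14:6 it is 8/20 = 0.40.

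**3. Average over randomisations.** Imbalance is equally likely in either direction, so the expected shift is zero. The variance of the contrast rises, however. The expected number of older subjects without an older block partner is 20 × 40/59 = 13.56, which is also the expected squared imbalance.

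- Variance of the contrast = 1/20 + δ² × 13.56/400.
- Relative increase = δ² × 13.56/20 = 0.678 δ².
- δ = 0.2: 2.7%. δ = 0.3: 6.1%. δ = 0.5: 16.9%.

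**4. Error rates.** Simulated paired t-test, 20 subjects, no lens effect, nominal 2.5% in one direction:

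| δ | 13:7, unfavourable direction | 13:7, opposite direction | Averaged over all splits |
|---|---|---|---|
| 0.2 | 4.1% | 1.2% | 2.4% |
| 0.3 | 5.0% | 0.8% | 2.4% |
| 0.5 | 6.2% | 0.3% | 2.2% |

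The averaged rate does not exceed 2.5% because an unadjusted right-left difference also widens the SD in the test's denominator.

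**5. After stratifying.** Separate lists in blocks of 2 split 20 older subjects 10:10 at randomisation (difference at most 1 if the number is odd), so the 17% becomes 0%. Without an eye-side term the test is then conservative: two-sided error was about 2.9% at δ = 0.5. With the term and no stratification, adjusting within the older group costs 1/(1 - 0.30²) = 1.099 at 13:7, about 10% more variance.

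**The case against.** **The lists may already be stratified.** Section 4.3 uses the word stratified, and no section says that the lists ignore age. This stands in part. The 2:1 ratio in 4.3 can only describe enrolment counts, since lens allocation is 1:1, but that lack of stratification is inferred from the silence of 5.1. The supportable statement is that the plan does not say.

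**A reader might infer that the design inflates false positives.** It does not. The raised rates in step 4 hold only after a 13:7 split in the unfavourable direction. The mirror-image split lowers them, and the average stays at or below nominal.

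**A right-left difference is assumed.** This stands. Both lenses are worn at once, so uneven eye side creates no imbalance in subject characteristics between lenses. The documents report no right-left difference. They also fix no order for testing the eyes, so such a difference can be neither sized nor excluded. The dominant-eye term, if coded per eye, would absorb whatever part follows dominance; 14.5 does not give the coding.

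**The within-age contrast is conditional.** Correct. It is made only if the interaction is significant. The default whole-sample contrast is balanced on eye side by the blocks of 2.

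**Activation order.** A reader might also infer harm from having no stated block for order at Visit 2. None is shown. All three tests are done in both rounds with values recorded for each eye, so a round effect common to both eyes cancels from a Test-Control contrast taken within a round.

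**Conclusion.** The concern holds as a minor point about precision and clarity. The plan enrols by age and may report by age, but does not say that eye side is balanced by age. On one shared list with random arrival, about one visit in six would have a 13:7 or worse split among 20 older subjects, moving that group's contrast by at least 0.30 of any right-left difference. There is no bias or type I error inflation over randomisations. The expected loss is about 3%, 6% or 17% in variance under assumed differences of 0.2, 0.3 or 0.5 SD, and nil if the eyes do not differ. It falls only on the older-group contrast and the interaction, and matters for reporting only if the interaction is significant.

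**What to change.** State in 5.1 whether the lists are stratified by age. If they are not, generate separate PROC PLAN lists for ages 18-39 and 40-65 at each visit, balancing eye side within each list. Preferably also add an eye-side (OD/OS) term to the models in 14.5 and 14.6, and state how dominant eye is coded. The term matters alongside stratification, because balance without it leaves the right-left variation in the residual and the test conservative. If the lists have already been issued, the term alone removes the shift. Blocks of 4 covering eye side by activation order at Visit 2 are optional.

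Cost: a few lines in the randomisation program and one model term; no extra subjects, visits or staff. Later dropout could reintroduce a small imbalance, and stratifying by age does not guarantee balance of Test lens against the dominant eye.
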